#### 4.5 Risk-to-benefit rationale

HA-based dermal fillers, such as saypha® VOLUME Lidocaine, are generally considered very safe and effective, and have been widely used for soft tissue augmentation worldwide. There is also no scientific evidence demonstrating adverse events of fillers or hyaluronidase in pregnant women. Observed adverse effects are mainly related to the injection procedure, are transient and mostly mild. While few serious adverse effects have been reported, these are very rare and not expected to occur when the device is correctly applied. This is supported by a remarkable safety track record of saypha® VOLUME, with few ADEs reported among almost 2 million units sold since 2009, combined with favorable safety data from one clinical trial.

The performance and safety of lidocaine-containing HA dermal fillers for correction of nasolabial folds have been well documented in medical literature, and saypha® VOLUME Lidocaine has been approved for use in this indication. Considering the potential benefits of correction, in particular the immediate and long-lasting improvement of distressing aesthetic defect, and the low risk of the treatment when used appropriately by an experienced user, the benefits clearly outweigh the potential risks.

Participation in any clinical trial is currently associated with increased risk and additional challenges due to the COVID-19 pandemic caused by SARS-CoV-2. First and top priority of CROMA-PHARMA GmbH and the safety of the subjects and all persons involved in the clinical investigation.

Both the European Medicines Agency (EMA) and the US Food and Drug Administration (FDA) as well as national health authorities in Europe have issued guidelines that aim to provide recommendations for conduct of clinical trials during the COVID-19 pandemic. Given the circumstances of the recurrently relapsing pandemic or dynamically evolving epidemic situation with regard to the spread of COVID-19, CROMA-PHARMA GmbH and statement will pay special attention to protect subjects participating in the investigation and clinical site staff involved in clinical investigations against infection with SARS-CoV-2 as requested by the EMA guidelines. Both, CROMA-PHARMA GmbH and statement, will continue to observe the situation with care and will re-evaluate and amend the risk mitigation measures, if deemed appropriate.

CROMA-PHARMA GmbH has evaluated all currently available safety data on saypha® VOLUME Lidocaine. Based on the local mode of administration once or twice, the low systemic exposure, and the safety profile, it is concluded that the treatment with saypha® VOLUME Lidocaine is not believed to put trial subjects under an increased risk for viral infections including SARS-CoV-2. At present, there is no change in the risk-benefit ratio foreseen that mandates any changes to the current protocol instructions.

However, the risk of exposure to infected people cannot be excluded as the subjects may need to expose themselves to public areas (e.g. commute to the investigation site) and have additional human contact (e.g. with clinical site staff). Appropriate risk assessments and mitigation measures will be considered to protect the health and well-being of involved persons and to ensure the integrity of the data obtained during the clinical investigation.

If site visits are not possible, safety data will be collected remotely by the Clinical Research Associate via telephone or electronic communication to ensure subject safety.

Investigators are responsible for taking appropriate measures to ensure the safety of individual subjects in accordance with preventive measures enacted by local authorities.

#### 4.6 COVID-19 pandemic contingency plan

Without compromising the safety of subjects and integrity of the investigation, it is expected that all efforts are made to secure attendance of subjects at the clinical investigation site for all visits, ensuring efficacy and safety assessments for the investigation. This includes but is not limited to complying with recommendations/regulations issued by local health authorities, the increase of protective safety and hygiene measures (e.g. mask obligation, hand disinfection, distance control) for both subjects and site personnel, and the regular monitoring of the health status of subjects. Those safety and hygiene measures will have no influence on the conduct of the investigation but are being implemented to minimize the risk of spread of COVID-19 infection.

To minimize exposure of subjects to public areas and transportation, CROMA-PHARMA GmbH is reimbursing the travel costs of subjects on their way to and from the investigation site when using a taxi.

It will be at the discretion of the investigator to decide whether subject on-site visits are considered necessary to ensure subject safety in periods when on-site visits are not interfering with the primary endpoint of the CIP (e.g. for visits 5, 7, 8-11). ). If deemed necessary, the investigator may provide a letter to the subjects on the way to sites explaining why commuting is required in this case.

If on-site visits are not possible due to preventive measures issued by city or local authorities or site obligations, the affected site will postpone on-site visits and will perform phone calls and collect safety and performance data to ensure subject safety as far as possible.

In general, more intense telephone contacts between clinical site staff and enrolled subjects will be utilized to closely monitor the situation and status of subject participation. In the eCRF, it will be recorded whether a given assessment was done remotely or not done. Any telephone contact or unscheduled visit will be recorded. For any of these records, it will be reported if this was due to the COVID-19 pandemic.

If a subject is tested positive for COVID-19, the investigator may withdraw the subject from further participation. The continuation may be decided in cooperation between the investigator and the sponsor if the subject recovers prior to the next scheduled visit. A COVID-19 infection will be documented as AE.

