# Synopsis

Investigation title	A prospective, randomized, multicenter study evaluating saypha ® VOLUME Lidocaine for the correction of nasolabial folds
Short title	SAVINO (SAypha Volume LIdocaine in Nasolabial FOlds)
Investigation ID	CPH-101-201477
Investigation sites	At least 3 sites located in Austria
Phase of development	Investigation according to § 40 (2) MPG
Aesthetic Indication	Moderate to severe nasolabial folds
Planned duration	The duration of the clinical investigation will be a maximum of 24 months for each participating subject. The total expected duration of the clinical investigation is about 27 months with an expected recruitment period of about 3 months. Recruitment halts due to COVID-19 pandemic lead to the prolongation of the recruitment period and the extension of the total duration of the clinical investigation. In case it is observed by the investigators that at a given visit no aesthetic effect is any more visible in approximately 75 % of the subjects, the study can be terminated at an earlier time point, but not before week 52.
Objectives	
 
To evaluate the performance of saypha® VOLUME Lidocaine for the correction of nasolabial folds using injection into the deep dermis or supraperiostal
 
To evaluate the safety and long term safety of saypha® VOLUME Lidocaine
 

	when used for correction of nasolabial folds
	To evaluate the duration of the aesthetic effect
Study design	A prospective, randomized, multicenter investigation. Following informed consent and screening, eligible subjects with moderate to severe nasolabial folds will be injected with saypha ® VOLUME Lidocaine into the deep dermis or supraperiostal, and will return for follow-up assessments at Week 2, 4, 24, 36, 52 and optional at Week 65, 78 and 104 after the treatment. A Touch-up treatment may be done at Week 2, if deemed appropriate by the investigator. The performance of the investigational device will be evaluated by the investigator by assessing severity of nasolabial folds using the Nasolabial Folds Severity Rating Scale (NLF-SRS) at Week 4, 24, 36, 52 after the treatment and optional at Week 65, 78 and 104 and in comparison to Day 0. Telephone visits will be performed approximately 24 hours post- administration to monitor possible adverse events. In case any adverse events are reported during the telephone visits an unscheduled visit should be performed.

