Investigational device and mode of administration	saypha ® VOLUME Lidocaine is a sterile, biodegradable, viscoelastic, transparent, isotonic and homogenized injectable gel implant formulated in a physiologic buffer to a concentration of 23 mg/mL, with addition of 0.3% lidocaine hydrochloride.

	saypha ® VOLUME Lidocaine is administered by injection into the deep dermis or supraperiostal. The volume applied depends on the size of the area which requires correction and will be selected by the investigator. It is recommended that a maximum volume of 4 ml per treatment is applied, but should not exceed 10 mL in total per treatment.
Treatment duration	A single application, with optional Touch-up treatment after two weeks, if the desired level of correction has not been achieved with the initial application
Primary performance endpoints	• The proportion of subjects with the NLF-SRS grade reduced by ≥1 point versus baseline at Week 24, within each manufacturing site, C1 and HQ, separately and for the whole analysis population
Secondary performance endpoints	The following secondary performance endpoints will be evaluated within each manufacturing site, C1 and HQ, separately and for the whole analysis population:
	• The average change versus baseline in the NLF-SRS grade at Week 4, Week 24, Week 36, Week 52 and, optional at Week 65, Week 78 and Week 104 as evaluated by the investigator
	• The proportion of subjects with the NLF-SRS grade reduced by ≥1 point versus baseline at Week 4, Week 36, Week 52 and optional at Week 65, Week 78 and Week 104
Exploratory performance endpoints	The primary and secondary performance endpoints will be evaluated within the subgroups defined by the injection technique and device, needle and cannula, respectively.
	The following endpoints will be assessed for the whole analysis population:
	• The proportion of subjects with the NLF-SRS grade reduced by ≥2 point versus baseline at Week 4, Week 24, Week 36 and Week 52 and optional at Week 65, Week 78 and Week 104.
	• The proportion of subjects with aesthetic improvement at Week 4, Week 24, Week 36, Week 52 and optional at Week 65, Week 78 and Week 104, as evaluated by the investigator using the Global Aesthetic Improvement Scale (GAIS)

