#### 6.1.7 Replacement of subjects

Subjects withdrawn from the investigation or lost for follow-up will not be replaced.

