#### 6.3.6 Withdrawal criteria and procedures

The subject may be withdrawn from the investigation for any of the following reasons:

- 1. Occurrence of an AE which requires a premature termination of the treatment or precludes followup of the subject
- 2. A major CIP deviation, which may interfere with evaluation of the treatment outcome (e.g., additional aesthetic correction of the defect during the course of the study, use of prohibited medication, or similar)
- 3. Investigator's decision, triggered by safety, behavioural or administrative reasons
- 4. Informed consent withdrawal

A subject is free to withdraw the consent and leave the investigation at any time with no obligation to specify the reason for withdrawal. Efforts should be made, however, to get in touch with subjects who did not attend the scheduled visit and clarify the reason for default.

Reasons, circumstances and findings related to early withdrawal should be fully described in the eCRF respecting the subject's rights. Attempts should be made to perform an early termination visit, which should consist of the assessments planned for the Week 104 visit. In the event that the withdrawal is caused by an AE, the procedures stated in Section 14.6 must be followed.

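### Protocol 4.6 and 6.3.6 allow a positive COVID-19 test or a major deviation to end all follow-up after a one-off treatment, with avoidable loss of Week 24 and late safety data

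*Protocol*

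**What the plan says.** **Treatment.** The Synopsis describes "A single application, with optional Touch-up treatment after two weeks". No study treatment is scheduled after that.

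**COVID-19.** Protocol 4.6: "If a subject is tested positive for COVID-19, the investigator may withdraw the subject from further participation". It continues: "The continuation may be decided in cooperation between the investigator and the sponsor if the subject recovers prior to the next scheduled visit".

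**Other grounds.** Protocol 6.3.6 lists reasons for which a subject may be withdrawn from the investigation. They include "A major CIP deviation, which may interfere with evaluation of the treatment outcome", with an additional aesthetic correction as one example, and "Occurrence of an AE which requires a premature termination of the treatment or precludes followup of the subject". A general item covers an investigator's decision for safety, behavioural or administrative reasons.

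**After withdrawal.** Protocol 6.1.7: "Subjects withdrawn from the investigation or lost for follow-up will not be replaced". Protocol 7.3 and SAP 3.5.1 rule out imputation. An early termination visit is to be attempted (Protocol 6.3.6 and 6.4.14, SAP 3.5.1). Known adverse events are followed under Protocol 14.6. SAP 3.5.1 assigns performance data taken at withdrawal to the nearest earlier visit that is still empty. SAP 3.5.2 only lists results that cannot be assigned to a planned visit.

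**The alternative already in the plan.** Protocol 6.1.6.6 and 6.4.15 provide for a delayed on-site visit with every assessment of the cancelled one, or a safety phone call. SAP 3.5.3 assigns the results to the cancelled visit.

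**Objectives.** The Synopsis includes "To evaluate the safety and long term safety of saypha" VOLUME Lidocaine. Protocol 5.1 adds the duration of the aesthetic effect.

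**The concern.** Neither document separates stopping treatment from stopping follow-up. In a trial with repeated dosing the two can be confused at little cost. Here, once the Week 2 touch-up has passed, there is nothing left to stop, and withdrawal only means that the subject is no longer observed.

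The COVID-19 rule also works against the rest of section 4.6, which asks for every effort to secure attendance. That section leaves the Week 24 visit out of its examples of visits that do not interfere with the primary endpoint.

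A major deviation needs no withdrawal to protect the analysis. SAP 3.3 already excludes from the per-protocol set subjects who had a procedure interfering with the Week 24 evaluation, and Protocol section 10 sends deviations to the data review meeting.

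At stake are the Week 24 response rate, the duration of effect and late safety. A subject who seeks another correction may well have an inadequate or fading result, so this loss could be informative.

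**Working it through.** **1. The plan's own figure.** Inputs from Protocol 7.1 and 6.3.1 and SAP 2.2: response 0.90, n = 50 per manufacturing site, two-sided 95% interval by normal approximation, 110 enrolled, about 10 drop-outs.

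Half-width = 1.96 × √(0.9 × 0.1 / n). With n = 50: 1.96 × 0.0424 = 0.0832, giving [0.817; 0.983]. This reproduces, and 110 − 10 = 100 gives 50 per manufacturing site.

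**2. Same infection, two routes.** Take a subject graded at Week 4 who tests positive shortly before Week 24.

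| Route | Rule | Week 24 grade |
|---|---|---|
| On-site visit postponed | Protocol 6.1.6.6, SAP 3.5.3 | Assigned to Week 24 and analysed |
| Phone call only | Protocol 6.1.6.6, SAP 3.5.3 | None; adverse events, medication, subject GAIS and FACE-Q are kept |
| Withdrawn, early termination visit done | SAP 3.5.1, 3.5.2 | None; no earlier visit is empty, so the grade is only listed |

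**3. Precision.** The documents give no rate for such withdrawals. I assume 5% to 10%.

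- *Inside the allowance (these are the only losses):* 110 × 0.05 = 5.5 and 110 × 0.10 = 11 lost. The remaining 104.5 to 99 subjects give 52.25 to 49.5 per manufacturing site. Half-widths: 1.96 × √(0.09/52.25) = 0.081 and 1.96 × √(0.09/49.5) = 0.084.
- *On top of the 10 drop-outs, all before Week 24:* 5% to 10% of the 100 leaves 95 to 90, or 47.5 to 45 per manufacturing site. Half-widths: 1.96 × √(0.09/47.5) = 0.085 and 1.96 × √(0.09/45) = 0.088.

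**4. Bias if the loss is informative.** Suppose 90% is observed in those with data, a fraction f of the 100 is lost in addition, and those lost respond at rate r (assumed 0.5 to 0.9). The rate in the 100 is 0.9(1 − f) + r·f.

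- f = 0.10: 0.81 + 0.05 = 0.86 at r = 0.5; 0.81 + 0.09 = 0.90 at r = 0.9.
- f = 0.20: 0.72 + 0.10 = 0.82 at r = 0.5; 0.72 + 0.18 = 0.90 at r = 0.9.

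**5. Safety follow-up lost by a subject withdrawn at Week 24.** To the last non-optional visit: 52 − 24 = 28 weeks. If all optional visits take place: 104 − 24 = 80 weeks.

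**The case against.** The other side has a good deal right.

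- **Discretion.** A reader might infer that the plan removes these subjects automatically. It does not: both sections say may, and 4.6 allows continuation after recovery.
- **Adverse events.** A reader might infer that any adverse event can end participation under the adverse-event ground. That ground covers only events that end treatment or preclude follow-up. The first limb hardly applies after Week 2, and in the second case follow-up is lost anyway. An ordinary event could be reached only through the general investigator's-decision item.
- **Discarded data.** Data collected before withdrawal stay in the intent-to-treat and safety sets, provided the set definitions are met. The early termination visit and the follow-up of known events recover more.
- **Sample size.** It is tempting to say that COVID-19 withdrawals both use up the drop-out allowance and pull the sample below 50 per manufacturing site. That counts the same losses twice. Inside the allowance, precision is essentially as planned.
- **80 weeks.** This is a ceiling. Weeks 65, 78 and 104 are optional, the study may end from Week 52, and so may an individual subject's participation once no effect remains (Protocol 6.4.7).
- **Visit assignment.** SAP 3.5.3 assigns assessments made between visits to the closest missing visit, which could be a later one. Someone might use it to move a withdrawal grade forward to Week 24. SAP 3.5.1 is the specific rule for withdrawal, however, and it points backwards.
- **Contaminated grades.** After an additional correction, later grades no longer reflect the device alone. If simply kept, they could inflate the response rate. This is a fair demand on any remedy.

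What remains is that these provisions do not supply a Week 24 grade for a subject who attended Week 4 and is withdrawn before Week 24, and that new late events are no longer sought at visits.

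**Conclusion.** The point holds as a cheap improvement to two permissive rules. It shows no error in the sample size calculation and no demonstrated loss of data.

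The effect on precision is minor: at most about half a point on the half-width per manufacturing site (8.3 to 8.8), and that only if a 10% loss is wholly additional and falls before Week 24. The more serious effects are possible bias and lost late-safety observation. Under 10% additional loss, an observed 90% could stand for a rate of 86% to 90%. That range rests on assumed loss and response rates, and the lower end requires those lost to respond at only 50%.

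The conclusion on the missing Week 24 value assumes that SAP 3.5.1 governs assessments made at withdrawal.

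**What to change.** - **Protocol 4.6 and 6.3.6:** state that a positive COVID-19 test, a protocol deviation or an adverse event is not in itself a reason to end follow-up. The subject stays in adverse-event and scheduled follow-up unless consent is withdrawn or follow-up is impossible.
- **Protocol 4.6:** for COVID-19, refer to the postponed on-site visit in 6.1.6.6 as the usual course, assigned under SAP 3.5.3. Note that a phone call is second best because it yields no NLF-SRS grade, which matters most at Week 24.
- **SAP 3.4.3.2:** state that NLF-SRS grades after an additional correction are flagged and do not count as response to the device. Say explicitly how such subjects enter the denominator and the mean-change summaries.

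This concerns data collection only; treatment decisions and care of adverse events are unchanged. The cost is protocol and SAP wording, continued contact with a few subjects, and some flagged grades to handle in the analysis.

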#### 5 Objectives and hypotheses of the clinical investigation

#### 5.1 Objectives

The objectives of this clinical investigation are:

- To evaluate the performance of saypha® VOLUME Lidocaine for the correction of nasolabial folds using injection into the deep dermis or supraperiostal.
- To evaluate the safety of saypha® VOLUME Lidocaine when used for correction of nasolabial folds.
- To evaluate the duration of the aesthetic effect.

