#### 2.1 Device description

saypha® VOLUME Lidocaine is a sterile, biodegradable, viscoelastic, clear, transparent, isotonic and homogenized injectable gel implant. The implant consists of HA obtained from *Streptococcus equi* bacteria, which is highly cross-linked using 1,4-butanediol diglycidyl ether (BDDE) and formulated to a concentration of 23 mg/mL in a physiologic buffer (phosphate buffer pH 6.8-7.4, sodium chloride) with supplementation of 0.3% w/w lidocaine hydrochloride.

The device packaging contains one prefilled syringe with 1.0 mL of the injectable gel implant, two 27G  $\frac{1}{2}$ " disposable sterile needles and a product leaflet.

saypha® VOLUME Lidocaine is a class III medical device, which also contains an active pharmaceutical ingredient, a well-known local anaesthetic lidocaine hydrochloride, as an ancillary substance. It is an absorbable soft tissue filler for injection into the deep dermis or supraperiostal and remains in long term contact with human skin and connective tissues. HA is a natural component of human skin, hence saypha® VOLUME Lidocaine is naturally absorbed, with the lifetime of the device anticipated to last up to 9 months after treatment. The ancillary component, lidocaine hydrochloride, is rapidly released from

the device after injection, and due to short half-life of around 90 minutes is quickly eliminated from the body.

The device is manufactured in compliance with EN ISO 13485:2016. No materials of human or animal origin are used during manufacture or as raw materials.

Saypha® VOLUME Lidocaine is designed for single use and upon opening should not be re-sterilized or reused.

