### 4 Risks and benefits of the investigational device and clinical investigation

#### 4.1 Anticipated clinical benefits

The treatment with saypha® VOLUME Lidocaine may remove or reduce a distressing aesthetic defect in subjects with moderate-to-severe nasolabial folds, thereby improving their psychological and social wellbeing. This is achieved by a minimally invasive procedure with a short downtime, which results in an immediate and long-lasting effect, persisting for 6-12 months.

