#### 6.1.4 Exploratory performance endpoints

The primary and secondary performance endpoints will be evaluated within the subgroups defined by the injection device, needle and cannula, respectively.

The following endpoints will be assessed for the whole analysis population:

- The proportion of subjects with the NLF-SRS grade reduced by ≥2 point versus baseline at Week 4, Week 24, Week 36 and Week 52 and optional at Week 65, Week 78 and Week 104.
- The proportion of subjects with aesthetic improvement at Week 4, Week 24, Week 36 and week 52 and optional at Week 65, Week 78 and Week 104 as evaluated by the investigator using the Global Aesthetic Improvement Scale (GAIS).
- The proportion of subjects with aesthetic improvement at Week 4, Week 24, Week 36 and week 52 and optional at Week 65, Week 78 and Week 104 as evaluated by the subject using the Global Aesthetic Improvement Scale (GAIS).
- Subjects' satisfaction with aesthetic outcome of the treatment at Week 4, Week 24, Week 36 and week 52 and optional at Week 65, Week 78 and Week 104 as evaluated by the subject.
- The average pain intensity during and after the treatment, as evaluated by the subject using an 11point Numeric Pain Rating Scale (NPRS) immediately after the last injection and 15 min. thereafter, respectively.
- The proportion of subjects with the NLF-SRS grade reduced by ≥1 point versus baseline at Week 4, Week 24, Week 36 and week 52 and optional at Week 65, Week 78 and Week 104 as evaluated by the independent reviewer of photographs.
- Percentage of subjects having an aesthetic effect at Weeks 24, Week 36, Week 52 and optional at Week 65, Week 78 and Week 104 based on the investigator's life assessment.

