3.2.1.5 Assessment of aesthetic effect

The investigator will assess whether the aesthetic effect is still present in the subject. A liveassessment of the treated areas will be performed and the treated areas will be compared to the subject's photographs obtained at the Baseline Visit. The presence of the aesthetic effect will be recorded as either "Yes" or "No".

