3.4.3 Performance analyses

3.4.3.1 Hypotheses

This is a non-comparative clinical investigation and does not entail formal hypothesis testing. All analyses will be done using descriptive statistics.

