• descriptive summary statistics for average change versus baseline in the NLF-SRS grade, evaluated by the investigator at Week 4, 24, 36, 52 and optional at Week 65, 78 and 104 after initial treatment,

Exploratory performance outcome measures

For exploratory performance outcome measures the following will be given for the whole analysis population:

- percentage of responders with a ≥2-point improvement over Baseline on the 5-point NLF SRS, based on investigator's live assessment at Week 4, 24, 36, 52 and optional at Week 65, 78 and 104 after initial treatment,
- percentage of subjects with aesthetic improvement using the 5-point GAIS (subjects who have been rated as "very much improved" or "much improved" or "improved"), based on investigator's assessment at Week 4, 24, 36, 52 and optional at Week 65, 78 and 104 after initial treatment, for each treatment location (right NLF, left NLF) separately and overall,
- percentage of subjects with aesthetic improvement using the 5-point GAIS (subjects who have been rated as "very much improved" or "much improved" or "improved"), based on subject's assessment at Week 4, 24, 36, 52 and optional at Week 65, 78 and 104 after initial treatment, for each treatment location (right NLF, left NLF) separately and overall,
- percentage of responders with a ≥1-point improvement over Baseline on the 5-point NLF SRS, based on evaluation by an independent reviewer of photographs for Week 4, 24, 36, 52 and optional at Week 65, 78 and 104 after initial treatment,
- descriptive summary statistics for extent of subject satisfaction with outcome of the treatment, as assessed by the Face-Q questionnaire "Satisfaction with Outcome" at Week 4, 24, 36, 52 and optional at Week 65, 78 and 104 after initial treatment,
- descriptive summary statistics for pain intensity, as evaluated by the subject using an 11point Numeric Pain Rating Scale (NPRS) immediately after the last injection and 15 min thereafter, at Day 0 and optional at Week 2.
- percentage of subjects having an aesthetic effect, based on the investigator's life assessment at Week 4, 24, 36, 52 and optional at Week 65, 78 and 104.

Subgroups by injection device and by injection technique for performance outcome measures For analyses by the injection device (needle, cannula) and by injection technique (retrograde,

bolus) the following will be given for the whole analysis population:

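### Duration of the aesthetic effect is an objective, but only per-visit percentages are planned: no duration estimate with a confidence interval, and the percentages after Week 52 can overstate persistence

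*Protocol*

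**What the plan says.** Protocol 5.1 gives three objectives: performance, safety, and "To evaluate the duration of the aesthetic effect". The synopsis repeats the third.

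The relevant measurement is the investigator's live comparison with the baseline photographs: "The presence of the aesthetic effect will be recorded as either" Yes or No (SAP 3.2.1.5). The protocol endpoint is exploratory: "Percentage of subjects having an aesthetic effect at Weeks 24, Week 36, Week 52 and optional at Week 65, Week 78 and Week 104" (Protocol 6.1.4). SAP 3.4.3.2 plans the matching "percentage of subjects having an aesthetic effect", and SAP 3.4 restricts exploratory performance analyses to the whole population. SAP 3.4.3.1 adds: "All analyses will be done using descriptive statistics". Neither document defines a time to loss of effect, a censoring rule or a median duration.

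Three further provisions bear on how the percentages behave:

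- Protocol 6.4.7 and a footnote to the SAP 2.3 schedule allow a subject who has no effect from Week 52 onward to be ended early. Protocol 6.4.7 also allows new injections at that point.
- Protocol 7.3 and SAP 3.5.1 rule out imputation. SAP 3.5.1 to 3.5.3 reassign withdrawal, out-of-window, unscheduled and COVID-delayed assessments to a missing visit.
- The denominator of the per-visit percentage is not stated.

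The protocol also gives two figures of its own: a device described "with the lifetime of the device anticipated to last up to 9 months after treatment" (2.1), and a treatment that "results in an immediate and long-lasting effect, persisting for 6-12 months" (4.1).

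**The concern.** A percentage at each visit describes persistence but is not a duration. A reader who wants the median must find the two visits between which the percentage crosses one half, and gets no interval around the answer.

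The larger worry is who remains in the table. After Week 52 the subjects who may leave are those already rated No. If the percentage is taken over subjects rated at that visit, these known losses leave numerator and denominator together, and the remaining group looks better than the cohort. The late visits, which exist to show how long the effect lasts, would then be the least reliable. A time-to-loss analysis avoids this, because a subject stopped after a No has already contributed the interval in which the effect was lost.

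**Working it through.** **1. The plan's own figure.** Protocol 7.1 and SAP 2.2 give a 95% interval for a Week 24 response of 0.9 with n = 50: 0.9 ± 1.96 × √(0.9 × 0.1/50) = 0.9 ± 0.083 = [0.817; 0.983]. This reproduces. No corresponding figure exists for duration.

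**2. What the visits can resolve.** Ratings at Weeks 24, 36, 52, 65, 78 and 104 leave gaps of 36−24 = 12, 52−36 = 16, 65−52 = 13, 78−65 = 13 and 104−78 = 26 weeks. At 4.35 weeks per month, 6 to 12 months is about Weeks 26 to 52, and 9 months about Week 39.

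**3. Effect of stopping subjects rated No (assumed numbers).** Of 100 subjects, 50 are rated No at Week 52 and all are stopped. Of the other 50, 10 lose the effect by Week 65.

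- Observed-case percentage at Week 65: 40/50 = 80%.
- True percentage: 40/100 = 40%.

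**4. Simulation.** All inputs are assumptions, since the documents give none beyond the 110 subjects and the visit weeks: Weibull loss times with shape 2, no recovery of effect, 200 runs per scenario. The table uses a true median of 58 weeks, 10% of visits missed at random, and percentages over subjects seen. The true median interval is Weeks 52 to 65.

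| Subjects stopped after No from Week 52 | Method | Week 65 | Week 78 | Week 104 | Median interval correct |
|---|---|---|---|---|---|
| (truth) | | 0.419 | 0.285 | 0.108 | |
| None | Per visit | 0.419 | 0.285 | 0.107 | 176/200 |
| None | Turnbull | 0.420 | 0.285 | 0.108 | 180/200 |
| Half | Per visit | 0.523 | 0.401 | 0.170 | 59/200 |
| Half | Turnbull | 0.421 | 0.289 | 0.111 | 163/200 |
| All | Per visit | 0.681 | 0.654 | 0.367 | 0/200 |
| All | Turnbull | 0.416 | 0.285 | 0.110 | 176/200 |

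The excess over truth is about 6 to 12 percentage points with half stopped and 26 to 37 with all stopped. With all stopped, the mean per-visit figure rises from 0.567 at Week 52 to 0.681 at Week 65, which is impossible for a loss that does not reverse.

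**5. Median before Week 52.** With an assumed median of 44 weeks, the percentages put the median in the right interval in at least 192 of 200 runs in every scenario, and Turnbull in at least 195. The later percentages are still inflated: at Week 65 the truth is 0.220, against 0.305 with half stopped and 0.493 with all stopped.

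**6. Randomly missed visits alone.** With 20% missed, no stopping and a 58-week median, neither method is biased. The standard deviation at Week 52 is 0.053 per visit and 0.050 with Turnbull.

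**7. The other possible denominator.** If the full ITT number were used and absent subjects counted as without effect, the error would run downward. With 10% missed at random, Week 65 would read 0.9 × 0.419 = 0.377.

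**The case against.** The study is descriptive and the objective asks only that duration be evaluated. Percentages with the effect at up to six visits form a coarse persistence curve. The plan also gives the NLF-SRS response rate of at least 1 grade at each visit to Week 104, with 95% intervals, overall and by manufacturing site. A reader might infer that the objective is left unanswered; the documents do not support that. What is missing is a duration estimate with its uncertainty. Such an estimate needs no hypothesis test, so the descriptive design does not rule it out.

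Other stronger readings also fail:

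- *The percentages have no confidence interval.* SAP 3.4.3.2 names intervals for NLF-SRS results only, but the general rule in SAP 3.4 may cover this percentage. Either way, it would be an interval for a percentage, not for a duration.
- *Missed visits discard much information.* No rule lets a Yes at a later scheduled visit inform an earlier missed one, but step 6 shows that the loss is negligible when visits are missed at random.
- *The protocol's duration figures cannot be checked.* The 9-month figure is a device lifetime, stated in the context of absorption. The 6 to 12 months nearly coincide with the Week 24 and Week 52 visits. Protocol 5.3, on claims to be verified, contains neither. Turnbull's method cannot locate a loss within a visit interval either.
- *The SAP dropped this objective, or wrongly omits results by manufacturing site.* SAP 1.2 lists endpoints and restates none of the three objectives. Whole-population reporting of this endpoint is prespecified in both documents.

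It is also fair that neither early-ending rule acts before Week 52, and that the 58-week scenario lies beyond the protocol's own 6 to 12 months. This limits the effect on the median but does not remove the inflation of the later percentages.

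**Conclusion.** The point holds in a limited form. One of three objectives has no planned duration estimate with a confidence interval, and the percentages standing in for it can overstate persistence after Week 52.

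The size depends on three things the documents leave open: how many subjects without effect are ended, which denominator is used, and when the effect is typically lost. If nobody is ended for loss of effect, there is no bias and the gain is a median with an interval. If many are ended and the typical loss comes after Week 52, the overstatement can reach tens of percentage points and move the apparent median to a later visit interval. If the typical loss comes before Week 52, the bracket for the median stands and the gain is again mainly the interval.

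The magnitudes are illustrations. They assume percentages over subjects rated at the visit and a loss that does not reverse. The primary Week 24 analysis is unaffected.

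**What to change.** Add to SAP 3.4.3.2, as the analysis of the duration objective:

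- **Variable:** time from Day 0 to loss of aesthetic effect on the investigator's live rating.
- **Censoring:** interval-censored between the last Yes and the first No; left-censored if the first rating is No; right-censored at the last Yes if no No is seen. Name the visit of the first rating: SAP 3.4.3.2 lists Week 4, while the SAP 2.3 schedule starts this rating at Week 24.
- **Later ratings:** exclude ratings after any re-injection. List a later return to Yes without reopening the interval.
- **Output:** Turnbull curve, and the median (or the visit interval containing it) with a 95% CI, for example by bootstrap, for the whole population. As an option, show the same descriptively by manufacturing site.
- **Per-visit percentages:** keep them and state the denominator. At each visit show how many subjects were rated, how many had been ended after a No, and how many were missing for other reasons.

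The cost is one extra analysis and one figure on data already collected, with no new visits and no change in sample size. The downside is the assumption that the first No marks the loss of effect, which a subjective rating may not always satisfy; the listing of returns to Yes shows how often it fails.
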